4.4 Inclusion Criteria for Study Entry

- 4.4.1 RPFNA performed within 6 months of the Study Entry Visit and in the follicular portion (day 1-10) of the menstrual cycle. Note that day 1 is defined as the first day of bleeding. For non-menstruating women, RPFNA during the follicular phase must be confirmed by hormone levels drawn on the day of RPFNA. Either clinical laboratory results are sent to Protocol Chair for assessment of menstrual cycle phase; or an additional frozen serum aliquot is sent to KUMC for assay of hormone levels and phase confirmation. Confirmation of follicular phase will be included in the eligibility report for the potential subject.
- 4.4.2 RPFNA specimen exhibits hyperplasia +/- atypia; Masood score of ≥ 13 with ≥ 500 cells on the cytology slide.
- 4.4.3 Ki-67 $\geq 2\%$ positivity (≥ 500 cells).
- 4.4.4 Willing to continue on the same or similar type of contraception during the 12 month course of study. If using non-hormonal contraception, continue that and if hormonal contraception continue that. If heterosexually active, must be agreeable to use some form of contraception during the trial unless husband or partner has had a vasectomy or subject has had uterus removed. Safety of SDG during pregnancy has not been documented.
- 4.4.5 Have reasonable organ function as documented by CBC and metabolic chemistry profile (within 3 months prior to Study Entry Visit).
- 4.4.6 Willing to undergo a history and physical at baseline and 12 months and be contacted periodically by the trial coordinator during the 12 month study period.
- 4.4.7 Willing to repeat RPFNA at 12 months following initiation of study agent.
- 4.4.8 Willing to have blood drawn at baseline and 12 months. If non-menstruating, an additional draw will be performed at approximately 11 months so as to predict when to perform the RPFNA
- 4.4.9 Able to understand and willing to provide informed consent for the RPFNA's and study participation.

4.5 Screening, Consent and Enrollment Process

- 4.5.1 Cohort and Accrual: Potential subjects will be screened in the Breast Cancer Prevention Center at the University of Kansas Medical Center (KUMC), Kansas City, Kansas; and at similar high risk clinics at collaborating institutions. Recruitment will be conducted over approximately 4.5 years for a total accrual of n=242.
- 4.5.2 Consent at KUMC: At KUMC, potential subjects will sign KUMC HSC#4601 consent for screening RPFNA procedure; subjects qualifying for randomization will sign the trial specific consent document.
- 4.5.3 Consent at collaborating sites: Collaborating sites may use the trial specific consent prior to screening RPFNA for obtaining biospecimens for baseline assays, or may use a separate approved research/clinical consent for that purpose.
- 4.5.4 All prospective subjects undergoing RPFNA for screening at collaborating sites will be registered in a site screening log by the site study coordinator or principal investigator. The study coordinator will assign a unique identifier from a pre-designated series specific to that institution. This identifier, which will include subject initials, serves as the subject "name" for screening purposes and along with the date will be attached to all subject related biospecimens sent to KUMC. A screening checklist will also accompany the screening RPFNA specimen. This will also be used for pre-enrollment blood, urine questionnaires, and data collection. No protected health information should be attached to these items.
- 4.5.5 Subjects may not be stratified and randomized until they have completed the entire eligibility process including RPFNA and collection of baseline biospecimens, and the site study coordinator has received confirmation from KUMC that the subject is tissue eligible, and for non-menstruating women that the RPFNA was performed in the follicular phase.
- 4.5.6 The RPFNA results provided to the site will include the cytomorphology descriptor (non-proliferative, hyperplasia, or hyperplasia with atypia), cytology index score and Ki-67 percent positive cells; as well as a statement that the subject is or is not eligible on the basis of RPFNA to be randomized and enrolled.
- 4.5.7 At that time subjects will have an on study visit scheduled at which the remaining clinical eligibility criteria will be confirmed; at least a spot urine (and preferably also a 10-12 hr overnight) urine, fasting blood, and a buccal swab for polymorphism testing will be collected (collection materials provided by KUMC), and baseline questionnaires will be completed.
- 4.5.8 Once all biospecimens have been collected, all questionnaires completed, and all eligibility criteria have been met, the subject may be randomized and a completed eligibility checklist communicated to the KUMC Project Manager. Subjects will not be considered enrolled on the intervention phase of this study until they have been randomized.
- 4.5.9 Subjects who have undergone RPFNA tissue screening and are not eligible or who have decided not to participate in the intervention phase prior to randomization will have the primary reason for non-participation recorded on the post-aspiration screening case report form.

4.6 ID Assignment and Randomization

4.6.1 Each site will have a series of unique study IDs that provide the study agent assignment. The site study coordinator will assign the subject the next available sequential study ID. All forms, questionnaires and biospecimens subsequent to randomization are to be labeled with this study ID as well as the date.

4.6.2 Each site investigational pharmacy will have a randomization schedule which has been prepared and provided by the Study Statistician. Study agent randomization to placebo or active SDG will be provided for each sequential post-randomization study ID number. Other than the investigational pharmacist(s) and the central biostatisticians, the enrolling site staff, the coordinating site staff, and subjects will be blinded as to the assignment to active agent or matched placebo.

4.6.3 For subjects not on oral contraceptives, sequential study ID numbers are assigned starting at X001 and then increasing (e.g., X002, X003, etc.). Subjects using oral contraceptives will be assigned a study ID number starting with the last number provided to the institution and then in decreasing order (e.g., X099, X098, X097, etc.).

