5.6 Blinding and Unblinding Methods

In the event of a serious adverse event or other circumstance requiring unblinding, in the opinion of the responsible physician, the site investigator will notify KUMC. The KUMC statistician will unblind the subject to the site investigator if necessary. If the treatment blind is broken, the reason and the date should be recorded and signed by the investigator.

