10.0 DATA MANAGEMENT

10.1 Source Documents and CRFs

Source documents will consist of CBC and chemistry profile clinical laboratory reports, and forms created specifically for this study that will capture information such as physical exam, phone contact information, adverse events, concomitant medications, demographics, etc. To the extent which possible, source documents (aside from reports) will be formatted to be similar to the CRF format, in order to make the transcription from source to CRF more reliable. Source document files/chart must be kept available at sites for monitoring visits during the conduct of the study through completion of data analysis.

Information for data analyses will be entered by site trial coordinators from source document onto Case Report Forms (CRFs). Data items from the CRFs will then be entered into the web-based CRIS study database.

Subsequently, the information entered into the database will be systematically checked by Data Management staff. Other errors or omissions will be entered on Data Query Forms, which will be returned to the site trial coordinators for resolution. Data queries must be addressed and returned to KUMC within 14 days of submission to site.

Laboratory data from RPFNA and blood analyses performed at KUMC or consulting sites will be entered in Excel spread sheets which can be merged with the database held at KUMC. The spread sheets, with confirming printouts, will be considered as source documentation.

All data collected for this trial will ultimately reside in a central database. There are appropriate checks (such as comparison of electronic files to validated paper printouts) on data accuracy and completeness for all sources of data. This is accomplished via inspection of summary reports prepared by the biostatistician for this project, [name].

When the database has been declared to be complete and accurate, the database will be locked. Any changes to the database after that time can only be made by joint written agreement between the Protocol Chair, the Trial Statistician and the Data Manager.

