10.2 Data and Safety Monitoring Plan

The Data Safety and Monitoring Committee (DSMC) of the University of Kansas Cancer Center will provide annual review of this trial

The DSMC monitors data management and subject safety. Subject accrual is reviewed annually by the Protocol Review and Monitoring Committee of the University of Kansas Cancer Center. The DSMC also provides advice on the overall conduct of the study. Meetings will be held on an annual basis. Interval conference calls may be conducted as required. The functions of the DSMC are primarily those of an overview nature in regard to both data and safety, as detailed below.

All data collected for this trial will ultimately reside in a central trial specific database. Data accuracy and completeness will be monitored via inspection of summary reports prepared for the DSMC by the biostatistician for this project.

The subject cohort consists of essentially healthy women who are defined as being at high risk for the development of breast cancer, but do not have any clinical evidence of or suspicion for an

existing malignancy. As such, side effects that might be due to the study intervention are expected to be minimal but should be easily identified and monitored.

In regard to adverse events (AEs) or serious adverse events (SAEs), it is not deemed necessary for the DSMC to address these for individual subjects. Rather, all grade 4 toxicities are reported as an SAE to the institutional review board immediately.

In addition to the functions performed by the DSMC, an External Advisory Board (EAB) will serve in a general advisory role in regards to assessing the progress that is being made on the study. Subject accrual rates, and specifically problems with accrual that might impact on the ability of the trial to be completed, can be addressed by the EAB. Likewise, the EAB may make suggestions on other aspects that would improve the quality of the trial. The EAB consists of two individuals with experience in clinical prevention trial: [name]., of Mayo Clinic, Rochester, MN; and [name], of Johns Hopkins University, Baltimore, MD.

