11.2 Statistical Analysis

All analyses will be intent-to-treat. All subjects randomized will be evaluable for safety and all subjects that have both a pre and post specimen are evaluable for efficacy. Primary analysis of efficacy will be performed on all evaluable subjects and secondary analysis will be done on those subjects who received at least 6 months of study medication and were confirmed as being in the follicular phase for both RPFNA procedures. From our experience we have very little missing data; however, if the missing data rate is above 5%, we will use multiple imputation to impute these values to perform the primary and secondary analyses.

The primary outcome will be change in Ki-67 (percent of cells expressing Ki-67) from baseline to 12 months. The two-sample t-test will be used to compare the change in Ki-67 between the SDG

and placebo groups. Any difference in baseline values of Ki-67 between the two groups would be due to chance, however, if there is a significant difference, then analysis of covariance adjusting for baseline values will be performed. Due to potential skewness in these variables we will assess whether or not the Central Limit Theorem may be assumed. Given the sample size the existence of an extremely high degree of skewness would require the use of the Wilcoxon Signed Rank test.

For the secondary endpoints, similar methods as above will be used to compare the treatment and control groups at two time points for all markers, i.e., serum hormones and clinical laboratory tests. We will also correlate change in the primary biomarker Ki-67 with change in other markers (e.g., bioavailable estradiol, cytokines, RTqPCR results) using Pearson's correlation coefficient. Again, if there exists a high degree of skewness in these variables, Spearman's correlation will be utilized.

Multiple regression analysis will also be used to investigate whether changes in Ki-67 are due to variables other than treatment effect (e.g., age, cytromorphology, Gail risk; as well as the predictive effect of other biomarkers on modulation of Ki-67). Best subsets and stepwise approaches will be employed while controlling for treatment group.

For comparison of moderate or worse toxicities we will consider grade 3 toxicity or premature trial discontinuation as the critical events. The prevalence of events in the SDG vs. the placebo arm will be examined by Fisher's exact test.

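### The central biostatisticians are unblinded and the switch from the primary t-test to a rank test has no criterion, so the plan allows the primary test to be chosen by someone who can see the arms

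*Combined protocol and SAP*

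**What the plan says.** **Masking.** Section 4.6.2 masks site staff, coordinating staff and subjects, and exempts two groups: "Other than the investigational pharmacist(s) and the central biostatisticians, the enrolling site staff, the coordinating site staff, and subjects will be blinded". The same section says each pharmacy holds a "randomization schedule which has been prepared and provided by the Study Statistician". On code breaks, section 5.6 says: "The KUMC statistician will unblind the subject to the site investigator if necessary".

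**Primary test.** Section 11.2 sets the default: "The two-sample t-test will be used to compare the change in Ki-67 between the SDG" and placebo arms. Three data-dependent branches follow.
- ANCOVA on baseline Ki-67, if the arms differ significantly at baseline. No significance level is given.
- A Wilcoxon test, if skewness is extreme. The text introducing it is: "Due to potential skewness in these variables we will assess whether or not the Central Limit Theorem may be assumed". There is no numeric criterion and no named decision-maker.
- Multiple imputation, if more than 5% of data are missing. This trigger is numeric, but no imputation model is given.

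**Data handling.** Section 10.1 describes accuracy and completeness checks: "This is accomplished via inspection of summary reports prepared by the biostatistician for this project". Section 10.2 uses similar words for the monitoring committee: "inspection of summary reports prepared for the DSMC by the biostatistician for this project". Changes after lock "can only be made by joint written agreement between the Protocol Chair, the Trial Statistician and the Data Manager".

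No section provides for a masked data review, or for a decision on the primary test that is recorded before the arms are visible.

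**The concern.** The trial has one primary comparison at two-sided 5%. If the choice between a t-test and a rank test is left to judgement, and the person judging can see which choice favours the study agent, the nominal 5% is no longer guaranteed. A result that is significant under one test and not the other could not be defended from the documents, however carefully the choice was made.

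The judgement is likely to be needed. Section 3.0 gives a pilot baseline Ki-67 mean of 6.4% against a median of 4%, section 2.4.4.2 gives a pilot baseline range of 2-16.8%, and section 4.4.3 excludes values below 2%. Right skew is to be expected. The named fallback also needs interpretation: the signed rank test is a paired test, whereas the comparison is between two arms.

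**Working it through.** **1. The plan's own power figure.** Inputs from 11.1 and 11.2: 220 evaluable at 2:1 (about 147 and 73), difference 2.5 points, SD of change 6, two-sided alpha 5%.
- Standard error = 6 × √(1/73 + 1/147) = 0.859.
- Standardised difference = 2.5 / 0.859 = 2.91.
- Power ≈ Φ(2.91 − 1.96) = 82.9%; with the noncentral t, 82.6%.

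The stated 83% is reproduced. The point below does not depend on it.

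**2. Who could choose the test, and with what in view.**

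| Step | Role named | Masked? |
|---|---|---|
| Prepares the allocation list (4.6.2) | Study Statistician | Not stated individually; has seen the list |
| Exempt from masking (4.6.2) | Central biostatisticians | No |
| Breaks codes (5.6) | KUMC statistician | Must have access to codes |
| Summary reports (10.1, 10.2) | Project biostatistician | Not stated |
| Post-lock agreement (10.1) | Protocol Chair, Trial Statistician, Data Manager | Chair and Data Manager masked if they count as coordinating staff |
| Judges skewness (11.2) | Not stated | Not stated |

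Nothing keeps an unmasked statistician away from the last row.

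**3. Size under the null.** The documents do not give the full Ki-67 distribution, so every figure here rests on assumed distributions. All runs use 147 vs 73 with no treatment effect, and a two-sample rank-sum test in place of the signed rank test, which does not compare two arms. The baseline trigger is taken as p < 0.05 because the plan gives no level.

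Main run: baseline Ki-67 truncated log-normal (mean 6.7, median 4.7), log-scale baseline-to-follow-up correlation 0, 0.3 and 0.5, 4,000 trials each. Monte Carlo standard error at a rate near 7% is √(0.07 × 0.93 / 4,000) = 0.4 points.

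| Procedure | Type I error |
|---|---|
| Baseline rule applied mechanically (ANCOVA if baseline p < 0.05, otherwise t-test), no rank test | 3.1-4.8% |
| Baseline rule respected, then the smaller p of that result and the rank test | 6.3-7.7% |
| Smallest p of t-test, ANCOVA and rank test | 9.3-10.0% |

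Other runs, under different assumed distributions, give the following.
- Two skewed distributions, 20,000 trials each: single tests 4.8-5.1%; mechanical baseline rule 3.7% and 4.5%; smallest of three 10.4% and 9.1%.
- Two normal distributions, 20,000 trials each: smallest of three 5.9% and 8.0%.
- Across all skewed runs, the smallest of three lies at about 9-11%.

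The inflation comes from free choice of the rank test with results in view. The written baseline rule does not produce it.

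**The case against.** **A statistician holding the list is normal.** That stands. The gap is the missing separation between list access and an undefined analysis choice.

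**A reader might infer that one unblinded statistician cleans the data, can change it after lock and picks the test.** The documents do not support this. They use five titles (Study Statistician, central biostatisticians, KUMC statistician, project biostatistician, Trial Statistician) and never say these are one person. Section 11.2 does not say who judges skewness. Section 10.1 gives systematic checking to Data Management staff and query resolution to site coordinators; the statistician prepares summary reports. Post-lock changes need two further signatories, who appear to be masked. Ki-67 is a consensus count by two technicians (Appendix 1, 5.3). No route to altering the endpoint is shown, so no additional post-lock sign-off is warranted.

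**A reader might infer that type I error doubles.** That figure treats ANCOVA as always available. Section 11.2 allows it only after a significant baseline difference, which at a 0.05 level occurs in about 5% of null trials. The rank test is likewise reserved for extreme skewness. Choosing the smallest p is conduct the plan does not describe. The 6-8% figure still assumes that the skewness judgement is made in whichever direction helps.

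**A reader might infer that double-blinding is lost.** Subjects, site staff and coordinating staff remain masked. The exposure is confined to the choice of analysis.

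**What stands:** the skewness trigger is undefined, nobody is named to apply it, and nothing requires it to be applied before the arms are visible.

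**Conclusion.** The point holds as a gap in the plan. It does not show biased conduct. The text permits an unmasked person to choose between the t-test/ANCOVA branch and a rank test after seeing the arms. If that freedom were fully used, type I error would be about 6-8% instead of 5%, with about 9-11% as an upper bound under skewed distributions if all three tests were open. If the baseline rule is followed mechanically, there is no inflation.

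These sizes assume skewed Ki-67 distributions chosen to resemble the pilot summary figures, a 0.05 baseline trigger and a rank-sum test as the fallback. That the person choosing is one of the unblinded statisticians is an inference the documents neither state nor exclude. The correction is worth making before any unmasked analysis because it is cheap and removes the question.

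**What to change.** **Section 11.2**
- Decide baseline adjustment now, for example ANCOVA on baseline Ki-67, instead of triggering it by a between-arm test. That trigger compares the arms, so pooled data cannot settle it.
- Settle the skewness/test decision and the imputation decision on pooled data without arm labels, in a record signed and dated before allocation codes are attached to the analysis file. State the skewness criterion, and name the fallback as a two-sample rank test.

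**Sections 4.6.2 and 5.6**
- State which existing central biostatistician holds the list and handles code breaks, and that this person does not make the decisions above.

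**Cost.** Mainly wording and one dated record. Section 4.6.2 uses a plural for the central biostatisticians, so separating the roles looks feasible. Sections 10.1 and 10.2 speak of a single project biostatistician, however; if there is in fact only one, some time from a second statistician would be needed. The sample size of 242 randomised and 220 evaluable, and the stated 83% power, do not change.

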5.0 AGENT ADMINISTRATION

5.1 Dose Regimen and Dose Groups

Both Brevail® and matched placebo are to be provided by Lignan Research, Inc. to the investigational pharmacy at each participating institution.

Brevail® (containing 50 mg of the active ingredient SDG) or placebo (containing the same filler material but without SDG) will be given to all trial participants for the 12 months of participation. All subjects should have off-study procedures no later than within 36 hours of the last dose of SDG or placebo. However, if a participant stops study agent prematurely in an unscheduled situation, she should come in for biomarker re-assessment as early as possible.

5.2 Study Agent Accountability

It is necessary to maintain a careful record of the inventory and disposition of all study agent using a drug accountability record form. The Investigational Pharmacy at each participating site is required to maintain adequate records of receipt, dispensing and final disposition of study agent. Include on receipt record from whom the agent was received and to whom study agent was shipped, date, quantity and batch or lot number. On dispensing record, note quantities and dates study agent was dispensed to and returned by each participant.

5.3 Packaging and Labels

Brevail® and matched placebo will be supplied by Lignan Research, Inc. in a form ready for dispensing. Each bottle of 100 capsules will be labeled with a label identifying study specific information, such as protocol number, dosing instructions, recommended storage conditions, randomization number, and a caution statement indicating that the agent is limited by United States law to investigational use only and the agent should be kept out of reach of children.

